7.7 Demographic and Other Baseline Characteristics

Descriptive statistics will be used to summarize demographic and baseline characteristic variables for FAS and PPS (baseline assessment on PPS will only be performed after evaluating the difference in sample size of FAS and PPS). This will include mean, standard deviation, median, IQR, minimum, and maximum for continuous variables, and counts and percentages for categorical variables. Demographic and Baseline variables will be collected through: Demographic information, Diagnosis History, Procedure, Audiograms, Speech Recognition Threshold and Word Recognition, Quality of Life Scores, Additional items and Patient Satisfaction. The following tables will be reported:

Table x - Subject Demographic Characteristics

Table x - Diagnosis History by Ear

Table x - Procedure information by Ear

Table x - Audiograms (Retrospective)

Table x - Speech Recognition Threshold and Word Recognition Score (Retrospective)

Table x - Quality of Life (APHAB) (Retrospective)

Table x - Additional Items (APHAB) (Retrospective)

Table x - Audiograms (Prospective)

Table x - Speech Recognition Threshold and Word Recognition Score (Prospective)

Table x - Quality of Life (APHAB) (Prospective)

Table x - Additional Items (APHAB) (Prospective)

Table x - ENT Exam

Listing x - Outcome (if ENT Physical Exam Ear or Skin over Implant Abnormal)

7.8 Treatment Characteristics

Duration of **Device Exposure** will be measured for FAS and PPS, in days starting from the implant through and including the time of last evaluation: Duration of device exposure (days) = (Study evaluation/explant date – Procedure date). Extent of device exposure will be presented in a summary table and supporting data listing.

Table x - Device Exposure

7.9 Interim Analyses

Interim analyses are not planned for this study.

7.10 Evaluation of Objectives

In this section, detailed information about each objective is included together with calculations and derivations of outcome parameters (see table in section 7.6), analysis methods, datasets analyzed (FAS or PPS) and additional analyses where applicable.

7.10.1 Primary endpoint

The primary safety endpoint is the proportion of AEs related to the Sophono implant or surgery, which will be assessed through retrospective surgical chart review and prospective ENT exam. The primary safety endpoint will be evaluated on FAS. The AEs used for this endpoint are according to Investigator's determination of the event's relatedness to the device or surgery.

Adverse Event rates will be displayed together with their 95% confidence interval (95%CI) overall, by site and by type of event.

A time to first Adverse Event will be performed using survival analysis. The analysis will be supported by a Kaplan Meier curve indicating the number of patients at risk and any possible comparison of curves between groups will be done using the Log-Rank Test where appropriate.

Table x - Primary safety endpoint – Sophono Implant related Adverse Events rates

Figure x - Kaplan Meier estimate of first Sophono Implant related Adverse Event occurrence

Table x - Kaplan Meier estimate of first Sophono Implant related Adverse Event occurrence

The primary effectiveness endpoint is the absolute difference (gain) in the free-field pure tone audiometry assessed by PTA unaided (AC) and aided by the Alpha 2 MPO processor. The primary effectiveness endpoint will be evaluated on PPS.

The difference between unaided and aided measurements will be analyzed by means of paired (samples) t-test or Wilcoxon signed rank sum test according to the normal or non-normal distribution.

Additional analysis will be performed on:

- the "within indication" subset will exclude from the analysis subjects whose Prospective AC & BC tests do not meet the device indications for use.

- The subsets defined by implanted ear diagnosis. For the subject affected by SSD, analyses will be performed for both the derived variables (both NR substitution methods).

Table x - Primary effectiveness endpoint - Difference in PTA between unaided (AC) and aided by the alpha 2 MPO Processor (Audiogram Results Gain)

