Safety Assessments	A review and assessment of all device-related Adverse Events (AE) collected retrospectively via chart review, and any prospective device-related AE that occur from the time of subject consent until the time of study exit.								
Statistics	
The primary effectiveness endpoints are the improvement in aided hearing from unaided hearing by the Sophono Alpha 2 MPO processor. This endpoint will be summarized by means of paired (samples) t-test or Wilcoxon signed rank sum test according to the normal or non-normal distribution as appropriate.
 
The primary safety endpoint is an assessment of all AEs (prospective or retrospective) that are directly attributable to the Sophono device (implant or processor). This endpoint will be the proportion of events reported with confidence interval (95%).
								

This document is electronically controlled. Printed copies are considered uncontrolled.

Confidential

5. Introduction

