6.1. Objectives

6.1.1. Primary Objectives

The primary objectives of this study are to

- Assess the safety of the Sophono implant
- Assess the effectiveness of the Sophono Alpha 2 MPO processor

in subjects diagnosed with CHL, SSD and mixed HL who currently has or has had the Sophono implant.

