6.2. Endpoints

6.2.1. Primary Endpoint

6.2.1.1. Primary Safety Endpoint

The primary safety endpoint is the proportion of AEs related to the Sophono implant, which will be assessed through retrospective surgical chart review and prospective ENT exam.

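### SAP 7.6 runs time to first adverse event backwards, and the primary safety endpoint is worded with conflicting attribution and as both a proportion and a rate

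*SAP*

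**What the plan says.** **Attribution.**
- The objective in Protocol 6.1.1 is "Assess the safety of the Sophono implant"; SAP 4.1 repeats it.
- The Protocol 4 synopsis (Statistics row) describes the endpoint as "an assessment of all AEs (prospective or retrospective) that are directly attributable to the Sophono device (implant or processor", closing the bracket there.
- Protocol 6.2.1.1: "The primary safety endpoint is the proportion of AEs related to the Sophono implant".
- SAP 7.10.1: "The primary safety endpoint is the proportion of AEs related to the Sophono implant or surgery". Two sentences later the investigator judges "relatedness to the device or surgery", while the output table is titled "Sophono Implant related Adverse Events rates".

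**Quantity.**
- All three definitions use the word proportion.
- The analysis sentence in SAP 7.10.1 reads "Adverse Event rates will be displayed together with their 95% confidence interval (95%CI) overall, by site and by type of event". It gives no denominator and no weighting.
- Protocol 13.3 has event rates weighted for centre, with exposure time running from implantation to the follow-up visit.
- Protocol 13.1 and SAP 6 size the study on a 14% incidence in 72 subjects, and Protocol 13.2 takes percentage denominators as subjects with available observations.

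**Time to first AE.**
- SAP 7.6 subtracts the first AE date from the study evaluation date.
- Protocol 13.3 runs survival time from implantation to the event or the last available follow-up.
- SAP 7.10 refers to the 7.6 table for derivations, and 7.10.1 plans a Kaplan-Meier curve for the first implant-related AE.

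**The concern.** A programmer who follows SAP 7.6 measures how long before the evaluation the event happened, not how long after implantation. Early events then appear late and late events early. Subjects with no AE have no event date to subtract, so the formula gives them no censoring time. The planned curve needs both.

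For the headline figure, the sentence that is followed decides whether processor and spacer events count, whether surgical events count, and whether the result is a share of subjects, a count of events or a rate over exposure. Two analysts could each follow the plan and report different numbers. No safety threshold is set, so the risk is an ambiguous estimate, not a wrong pass/fail decision.

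**Working it through.** **1. The plan's own precision.** Inputs from Protocol 13.1: p = 0.14, n = 72, 95% confidence, stated precision 9 points (5% to 23%).
- Wald: 1.96 × √(0.14 × 0.86 / 72) = 0.080, or 6.0% to 22.0%.
- With continuity correction: 0.0801 + 1/144 = 0.0871, or 5.3% to 22.7%. This rounds to the stated figures.
- Exact (Clopper-Pearson) for 10/72 = 13.9%: 6.9% to 24.1%, half-width 8.6 points.
- Dropout: 72 / 0.75 = 96, stated as about 100.

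The sample-size statement therefore stands as a calculation on subjects.

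**2. The time formula.** Let implantation be month 0 and evaluation month 24 (assumed).

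| First AE | Protocol 13.3 | SAP 7.6 |
|---|---|---|
| month 1 | 1 − 0 = 1 | 24 − 1 = 23 |
| month 18 | 18 − 0 = 18 | 24 − 18 = 6 |
| none | censored at last follow-up | no value |

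The effect on the curve can be illustrated with assumed data: 72 subjects, all followed to month 24, first AEs at months 1, 1, 1, 2, 2, 2, 3, 3, 12 and 18. Event-free subjects are censored at month 24, a rule that SAP 7.6 does not supply.
- From implantation, incidence at month 6 is 8/72 = 11.1%.
- Under SAP 7.6 the times become 23, 23, 23, 22, 22, 22, 21, 21, 12 and 6, so incidence at month 6 is 1/72 = 1.4%.
- At month 24 both give 10/72 = 13.9%.

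The shape is wrong while the end point agrees, so the total would not reveal the error. The other device durations in SAP 7.6 (device exposure, time to explant) do subtract the procedure date.

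**3. The endpoint wording side by side.**

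| Place | Attribution | Quantity |
|---|---|---|
| Protocol 4 | implant or processor | proportion of events |
| Protocol 6.2.1.1 | implant | proportion of AEs |
| Protocol 13.3 | not stated | centre-weighted rate, with exposure time |
| SAP 7.10.1 text | implant or surgery; device or surgery | proportion of AEs, then rates |
| SAP 7.10.1 titles | implant | rates |

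SAP 7.13 allows the SAP to differ from the protocol but does not record that the centre weighting was dropped.

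**4. Why the quantity matters.** Assume 10 of 72 subjects have 15 events between them.
- Proportion of subjects affected: 10/72 = 13.9%.
- Events per subject: 15/72 = 0.208.
- Events per subject-year at a mean exposure of 12, 24 or 36 months: 15/72 = 0.208, 15/144 = 0.104, 15/216 = 0.069.

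Only the first is on the same scale as the planned 14% incidence. The counts and exposures are assumptions that show the spread; they do not show that the planned precision fails.

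**The case against.** The strongest reply is that the intended estimate can be inferred. Protocol 13.1 and SAP 6 speak of incidence in 72 subjects, Protocol 13.2 gives subjects as the percentage denominator, the Full Analysis Set is a set of patients, and the Kaplan-Meier shows patients at risk. This largely stands for the denominator. A reader might infer that the unit is stated nowhere, and the documents do not support that. What they leave open is the numerator (events or affected subjects) and how a subject with bilateral implants, allowed by Protocol 7, is counted.

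Three other stronger readings also fail:
- *The proportion would be near 100% because only related AEs are collected.* Protocol 10.6, 12.1 and part of 12.2 do limit collection. But Protocol 12.1.1 says relatedness does not decide what is reported, and Protocol 12.2 has subjects asked about any AEs at the visit.
- *Counting events breaks the planned precision.* That depends on assumed repeat events and on how many subjects contribute, and it can go either way.
- *The relatedness cut-off is wholly undefined.* Protocol 12.1.1 puts uncertain events under 'possible' and says uncertainty should not exclude relatedness. This leans towards counting that grade, although no section says so outright.

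It is also fair that the mixed Poisson model is planned only for comparisons, and that the separate table specification named in SAP 10.1, which was not available, may define the rate. It could not reconcile conflicting endpoint text in the protocol and SAP.

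**Conclusion.** Both parts hold. The SAP 7.6 derivation is wrong as written: it contradicts Protocol 13.3, reverses the order of events and leaves event-free subjects without a time. In the assumed illustration, six-month incidence falls from 11.1% to 1.4%. A reader might infer that the headline safety figure is also corrupted; it is not, because the proportion does not use this variable.

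The endpoint wording conflicts on attribution and on proportion versus rate, and this changes which events are counted and what is estimated. The gap is one of definition. The stated precision reproduces at subject level and the sample size needs no change. The conclusion rests on the text of the two documents; only the illustrations rest on assumed data.

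**What to change.** **SAP 7.6.** Define time to first AE as first AE date minus procedure (implantation) date. Censor event-free subjects at the last available follow-up, as in Protocol 13.3, using the chart-review date for subjects with chart data only. State how explants are handled and make this consistent with the device-exposure definition in SAP 7.6 and 7.8, which can end at explant.

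**Protocol 4, Protocol 6.2.1.1 and SAP 7.10.1 (text and titles).**
- State the primary estimate as the proportion of Full Analysis Set subjects with at least one related AE. Count each subject once, including bilateral cases, with a named binomial 95% interval. This matches the basis of the sample size.
- Settle one attribution scope that fits the stated objective. Tabulate implant-, processor/spacer- and surgery-related events separately where the case report form allows.
- State that 'possible' and higher grades count as related, consistent with Protocol 12.1.1.

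**Supporting analyses.** Keep the exposure-based event rate and the Kaplan-Meier curve as supporting, and record in SAP 7.13 that the centre weighting was dropped.

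**Cost.** Wording in the named sections, one corrected formula and one extra table. The documents do not show whether the form records the component involved; if it does not, a listing review or an added field is needed. The downside is that a crude proportion ignores differing lengths of exposure, which the supporting rate and curve address.

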6.2.3. Other Endpoints

Other endpoints include:

- Change over time in speech reception threshold scores in the Sophono Alpha 2 and Alpha 2 MPO
- Change over time in word recognition scores in the Sophono Alpha 2 and Alpha 2 MPO

This document is electronically controlled. Printed copies are considered uncontrolled.

Confidential

7. Study Design

This study is an ambispective, multi-center, single-blind, intra-subject controlled study to assess safety of the Sophono implant and effectiveness of the Sophono Alpha 2 MPO processor in subjects with single-sided deafness (SSD), CHL, and mixed HL. This study will enroll approximately 100 subjects (with unilateral or bilateral implants) at up to 15 investigational sites in the US. (Investigational sites may include separate Audiology Centers, if applicable).

The subject population includes any patient who currently has or has had the Sophono implant, including those patients who have been explanted.

The study will consist of a retrospective medical chart review to collect data on AEs for all subjects upon receiving informed consent. A prospective clinic visit for subjects still implanted with the Sophono implant will be conducted to evaluate the subject's implant site and conduct hearing tests, along with a QOL and satisfaction self-assessment.

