9.3. Inclusion Criteria

- Any subject who currently has or who has had the Sophono implant (including those who have been explanted)
- Has or has had Sophono implant for 3 months or longer

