An anticipated adverse event is defined as an AE, the nature, severity, or degree of incidence of which is known and identified in applicable product labeling, published literature or the Investigational Plan or Informed Consent.

Based on event reports through literature review (15-19) anticipated Surgical Related AE's possibly noted in the Operative Report during the retrospective medical chart review should be reported on the appropriate CRF. These events may include:

This document is electronically controlled. Printed copies are considered uncontrolled.

Confidential

Table 4. Surgical Related Adverse Events

Event
Excessive Bleeding
Rupture of Dura
Cerebrospinal Fluid (CSF) Leak
Anesthesia Related Complications

Anticipated Post-operative Related AE's possibly seen in the retrospective medical chart review or at the office visit and their reportability within the study may include:

Table 5. Post-Operative Related Adverse Events

Event	Reportable Criteria
Abscess	Requiring medical intervention
Bleeding	Requiring medical intervention
Dehiscence (at Incision Site)	Requiring medical intervention
Depilation (Loss of Hair at Implant Site)	Excessive or cosmetically bothersome
Hematoma	Requiring medical intervention
Hyperemia	Excessive or requiring medical intervention
Infection (i.e. Cellulitis, Bacterial, etc.)	Requiring medical intervention
Inflammation/Skin Irritation (Redness)	Holger 2, 3, 4
Numbness (Hypoesthesia)	Notable or bothersome to subject

This document is electronically controlled. Printed copies are considered uncontrolled.

Confidential

Pain (Local)	Prolonged surgical procedure pain or pain lasting more than 10 days
Pressure (at the Implant Site)	Feeling of pressure continuing after subject begins using the processor
Scarring	Abnormal or Hypertrophic
Skin Necrosis (Pressure)	Requiring medical intervention
Swelling	Continuing after subject begins using the processor

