13.1. Sample size

Since the primary endpoint is composed of a safety and efficacy endpoint, the sample was determined by the primary objective on safety because it requires the larger sample size. An approximate total of 100 subjects will be enrolled.

Sample size on safety

The sample size calculation was estimated using data from previous studies with a precision-based calculation. (20, 21) Recent data have shown that 15.2% of percutaneous implants are lost in children and adverse skin reactions were found in 7.8 % during follow-up visits. (21) Using this information and assuming a lower incidence of implant loss in transcutaneous devices (19, 22, 23) and a lower incidence of skin reaction (18, 24), a minimum incidence of 14% of any adverse events with a sample size of 72 subjects will be able to obtain a 95% confidence level with a precision of +/- 9% (ranging from 5% to 23%). Considering a 25% withdrawal or potential dropout rate, a total of approximately 100 subjects will be enrolled.

Sample size on efficacy

It is expected that at least 6 paired subjects with the pure tone audiometry evaluation will be needed in order to demonstrate a difference in means between unaided and aided measurements in Hearing Improvement measured as PTA. From a literature search we found that studies have shown an average of 50% improvement on hearing measured as PTA.(13, 20, 21, 25-34) In the paper of Siegert (34) the mean and standard deviation of pure tone audiometry in 21 patients was 58.7 ± 8.2 dB HL unaided and 29.7 ± 8.2 dB HL aided. Based on these values, alpha level 5%, power 95% and two-sided test, a total of 6 paired subjects are needed.

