5.3 Overall study design and plan-description

After informed consent is collected, the study will consist of a retrospective medical chart review to collect data on AEs for all subjects. A prospective clinic visit for subjects still implanted with the Sophono implant will be conducted to evaluate the subject's implant site and conduct hearing tests, along with a QOL and satisfaction self-assessment.

All subjects will be screened for study eligibility. A qualified member of the investigational site's research team will review the inclusion and exclusion criteria to screen each subject. Subjects will be considered enrolled into the study when they have both:

[figure not shown]
- Been informed of the study design, objectives, risks and benefits
- Confirmed interest in participation by signing an IC and Research Authorization Forms

Any subject who currently has or who has had the Sophono implant (including those who have been explanted) may be enrolled.

A Screening and Enrollment Log will be maintained for all subjects. For screen-fail subjects, a reason for failure will be noted.

Clinical data will be collected during:

- a retrospective review of the subject's medical chart will be performed to gather and report data on subject surgical history, reportable AEs from the time of implantation to time of chart review, previous QOL scores, and previous audiometric testing results for the Sophono processors.
- an in-office ENT exam will be conducted to gather and report data on the ear and implant site for skin complications, potential AEs and Sophono system satisfaction and QOL questions. During the in-office visit Audiology testing will be performed to collect data on: Basic Sound Field Audiology thresholds at octave intervals, Speech Reception Threshold, Word Recognition Thresholds and Hearing in Noise.

Figure x – Flow Chart

Data collection requirements are summarized in the following table:

Table x – Data Collection Requirements

Data	Baseline	Retrospective	Prospective	Study Exit
Informed Consent	X			
Inclusion/Exclusion Criteria Evaluation	X			
Demographic	X			
Medical History (including Procedure)	X	X		
Audiogram		X	X	
Speech Recognition Threshold		X	X	
Word Recognition Threshold		X	X	
Quality of Life Scores (including Additional Items)		X	X	
Product Satisfaction			X	
ENT Exam			X	
Adverse Events		X	X	X
Protocol Deviations	X		X	X

6 Determination of Sample Size

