7.1.3 Analysis Set

The following subject set will be used for the analysis:

- The Full Analysis Set (FAS) includes **all** patients enrolled in the study who sign Patient Informed Consent and fulfill the inclusion and exclusion criteria. The FAS will be used to evaluate the primary safety endpoint.
- The Per Protocol Set (PPS) includes all patients enrolled in the study who sign Patient Informed Consent, fulfill the inclusion and exclusion criteria, and perform prospective activities. The PPS will be used to evaluate the primary effectiveness endpoint and secondary endpoints.

The following table shows how each population set will be used for analyses:

Table x – Analysis steps by population set

Population set	Baseline assessment*	Primary Safety Endpoints	Primary Effectiveness Endpoints	Secondary Endpoints
FAS	✓	✓		
PPS	✓		✓	✓

*According to the clinical study team, baseline assessment on PPS will only be performed after evaluating the difference in sample size of FAS and PPS.

For those patients who drop out of the study, the analyses will include all data up to the point of their last data collection.

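### The safety analysis pools chart-detected and visit-detected adverse events on the FAS, so events found only at the ENT visit are understated in proportion to missed visits

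*SAP*

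**What the plan says.** SAP 7.10.1 defines the primary safety endpoint as a proportion of AEs related to the implant or surgery, "which will be assessed through retrospective surgical chart review and prospective ENT exam. The primary safety endpoint will be evaluated on FAS". AE rates with 95% intervals are to be shown overall, by site and by type of event.

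SAP 7.1.3 puts in the FAS all "patients enrolled in the study who sign Patient Informed Consent and fulfill the inclusion and exclusion criteria". The PPS adds the requirement that subjects "fulfill the inclusion and exclusion criteria, and perform prospective activities", but it is used for effectiveness and secondary endpoints, not for safety.

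The visit is not for everyone. SAP 5.3 states: "A prospective clinic visit for subjects still implanted with the Sophono implant will be conducted to evaluate the subject's implant site". Protocol section 7 says the same, while Protocol 9.3 admits explanted subjects. Under Protocol 10.4, chart data are still analysed for subjects who decide against the visit. Protocol 10.9 allows retrospective safety data from subjects lost to follow-up to be used. SAP 7.4 rules out imputation.

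Protocol 12.2 describes two opportunities to collect AEs: the chart review, and the visit, where staff examine and question the subject. Some Table 5 criteria rest on that contact. Numbness, for instance, is reportable when "Notable or bothersome to subject", and skin irritation when it reaches Holger grade 2 or above.

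On sample size, Protocol 13.1 takes 72 subjects at 14% incidence and adds: "Considering a 25% withdrawal or potential dropout rate, a total of approximately 100 subjects will be enrolled".

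**The concern.** The endpoint has two sources of ascertainment, and part of the analysis set has only one. A still-implanted subject who never attends can contribute an event only if someone wrote it in the chart. A mild or symptom-based local event that would have come to light only on examination or questioning is not recorded for that subject. With the FAS as denominator, the subject then counts as free of that event although nobody looked.

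This error runs towards a lower rate, in a study meant to document safety. It falls mostly on the local and skin events in the by-type display, which SAP 7.10.1 makes part of the primary safety output. The interval for such events is also narrower than the number of examined subjects supports.

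**Working it through.** **Inputs from the documents.** Incidence 14%, 72 subjects, precision ±9% (5% to 23%), 25% withdrawal or dropout allowance, about 100 enrolled (Protocol 13.1; SAP section 6).

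**Inputs not in the documents, so assumed.** The actual proportion missing the visit (d), and the share of the overall proportion that rests on visit-only events (s), meaning subjects with an event who have none in the chart. Attendance is taken to be unrelated to event risk.

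**1. The plan's own figure.** The continuity-corrected normal half-width at n = 72 is 1.96 × √(0.14 × 0.86 / 72) + 1/(2 × 72) = 0.0801 + 0.0069 = 0.087. The interval is 5.3% to 22.7%, which rounds to the stated 5% to 23%. Enrolment is 72 / (1 − 0.25) = 96, given as about 100. So the planned precision rests on 72 subjects after dropout. The FAS would keep subjects who drop out after consent, provided they meet the entry criteria.

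**2. An event type found only at the visit.** If a fraction 1 − d of the FAS is examined, the reported rate is the rate in examined subjects × (1 − d), a relative understatement of d.

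| Proportion missing the visit (d) | Relative understatement |
|---|---|
| 5% | 5% |
| 10% | 10% |
| 15% | 15% |
| 25% (whole allowance is missed visits) | 25% |

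As an illustration with an arbitrary count, take 10 visit-only cases among 72 examined subjects. That is 10/72 = 13.9% (Wilson 95% CI 7.7% to 23.7%). On 96 subjects it is 10/96 = 10.4% (5.8% to 18.1%). The ratio is 72/96 = 0.75. The interval narrows from 16.0 to about 12.4 percentage points without any more subjects having been examined.

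**3. The overall proportion.** Chart-detected events are sought in everyone, so only the visit-only share is diluted: reported = 14% × (1 − s × d).

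| s | d = 10% | d = 25% |
|---|---|---|
| 10% | 13.9% | 13.7% |
| 25% | 13.7% | 13.1% |
| 50% | 13.3% | 12.3% |

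At d = 25% the relative loss is s × d, that is 2.5%, 6.25% and 12.5%.

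**The case against.** Several points on the other side have weight.

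- **A denominator rule exists.** Protocol 13.2 bases percentages on subjects with available observations unless otherwise stated, and SAP 7.10.1 names the FAS without spelling out a denominator. The detailed table specifications are in a separate document (SAP 10.1). This makes the FAS head count the natural reading, not a certainty. It does not cure the problem, because an AE that nobody looked for leaves no missing-value flag.
- **Other outputs help in part.** SAP 7.7 plans an ENT exam table and a listing of abnormal findings, and the Kaplan-Meier analysis can censor subjects at last follow-up. Neither changes the denominators in the AE rate table.
- **The affected group is limited.** Protocol 9.4 excludes implanted subjects unwilling or unable to do audiologic testing, and the FAS requires eligibility. What remains is mainly later withdrawals and losses, whose number is unknown.
- **Charts may hold some of these events.** Protocol 12.1.1 introduces Table 5 as events that may be seen in the chart or at the visit, so not every Holger 2 reaction or numb area is visit-only.

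Two stronger readings are tempting. A reader might infer that the whole endpoint is diluted by a quarter or more. The documents do not support this. The dilution applies only to visit-only events, and going beyond 25% would need explanted subjects on top of the allowance; their share is not given and they may already be inside it. A reader might also infer that explanted subjects are the main source of dilution, or had the most local trouble. But they have no implant in place to examine, their events from the implant period are sought in the chart, and nothing in the documents describes their event burden. Symptoms that only questioning would reveal could still be missed in them.

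**Conclusion.** The mechanism follows directly from the text: two sources, one analysis set, and a second source that part of that set does not have. By-type rates of visit-only events are understated by the proportion missing the visit. That is about 25% if the entire planning allowance turns out to be missed visits, and 5% to 15% if only 5% to 15% miss it. The effect on the overall proportion is modest: 14% becomes about 13.7% to 12.3% at 25% non-attendance with 10% to 50% visit-only.

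These sizes assume that attendance is unrelated to event risk and that the denominator is the FAS subject count. The firmest case is the still-implanted subject without a visit. This is a cheap improvement to reporting; it does not invalidate the safety analysis.

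**What to change.** In SAP 7.10.1:

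1. Keep the FAS analysis as primary and state its denominator.
2. In the by-type table, report chart-detected events on the FAS and visit-detected events on subjects who had the ENT exam.
3. Add a sensitivity analysis of the combined proportion in still-implanted subjects who had the ENT exam. Report explanted subjects separately on chart data. A combined rate limited to subjects with both sources would otherwise drop every explanted subject, so it should not replace the FAS figure.
4. Add a note that the FAS figure may understate events found only at the visit.

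No new data are needed, because retrospective and prospective AEs are already collected separately (Protocol 10.6 and 12.2; SAP 5.3). The cost is SAP wording, extra table columns, and a somewhat higher rate with a wider interval for visit-detected events.
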